6.1 Safety Endpoints

The safety and tolerability of AK002 will be assessed by determining the following:

- Symptom-directed physical examination
- Changes in body weight and vital signs
- Hematology
- Changes in concomitant medication use due to AE
- Blood chemistry
- Urinalysis
- Anti-drug antibodies
- Adverse events

6.2 Pharmacokinetic Endpoints

Blood (serum) will be collected for assessment of AK002 concentrations using a validated enzyme-linked immunosorbent assay (ELISA) method. Pharmacokinetic (PK) blood samples will be obtained predose on Extension Day 1 (if not already collected for AK002-016 last study visit), predose on Extension Day 197, and also on Extension Day 512 (± 3) or 35 (± 3) days after last dose of study drug, if ET, for assessment of AK002 concentrations.

Blood (serum) will be collected for assessment of ADA using a validated assay method. The ADA blood samples will be obtained predose on Extension Day 1 (if not already collected for AK002-016 last study visit), predose on Extension Day 197, and also on Extension Day 512 (± 3 days) or 35 (± 3) days after last dose of study drug, if ET, for assessment of ADA. Extra blood (serum) samples may also be drawn for assessment of ADA, in case of an immunogenicity-suspected AE.

6.3 Efficacy Endpoints

Daily self-administration of a disease-specific Patient Reported Outcome (PRO) questionnaire will be used to evaluate signs and symptoms associated with EG and/or EoD. The PRO Total Symptom Score (TSS) will be used to evaluate efficacy and comprises 6 symptoms, as listed below:

- Abdominal pain intensity
- Nausea intensity
- Fullness before meal intensity
- Loss of appetite intensity
- Bloating intensity
- Abdominal cramping intensity

Changes in quality of life will be measured by the Short-Form Health and Well-Being Survey (SF-36) questionnaire. Changes in the number of eosinophils in gastric and/or duodenal mucosa from baseline will also be evaluated.

6.4 Pharmacodynamic Endpoints

Change in blood eosinophils will be assessed at study visits.

7. Patient Selection

7.1 Number of Patients

Up to approximately 183 patients could be enrolled in Study AK002-016X, based on the enrollment of Study AK002-016.

7.2 Study Population

Patients who complete Study AK002-016 or Study AK002-012 and meet the inclusion criteria in Section 7.3 and none of the exclusion criteria in Section 7.4 will be eligible for enrollment.

7.3 Inclusion Criteria

Patients are eligible for the study if all of the following criteria are met:

- 1) Provide written informed consent.
- 2) Completed Study AK002-016, defined as having received 6 infusions of study drug and followed through at least Day 176 (± 3) or completed Study AK002-012, defined as having received the cohort-appropriate number of doses and followed for 5 months after last dose of study drug.
- 3) If patient is on preexisting dietary restrictions, willingness to maintain those restrictions, until the seventh dose has been received. After the seventh dose, diet may be liberalized.
- 4) Able and willing to comply with all study procedures.

- 5) Female patients must be either postmenopausal for at least 1 year or surgically sterile (tubal ligation, hysterectomy, or bilateral oophorectomy) for at least 3 months, or if of childbearing potential, have a negative pregnancy test and agree to use dual methods of contraception or abstain from sexual activity until the end of the study or for 120 days following the last dose of study drug, whichever is longer.
- 6) Male patients with female partners of childbearing potential must agree to use a highly effective method of contraception (vasectomy is acceptable) until the end of the study or for 120 days following the last dose of study drug, whichever is longer. All fertile men with female partners of childbearing potential should be instructed to contact the Investigator immediately if they suspect their partner might be pregnant at any time during study participation.

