	
5) Female patients must be either postmenopausal for at least 1 year or surgically sterile (tubal ligation, hysterectomy, or bilateral oophorectomy) for at least 3 months, or if of childbearing potential, have a negative pregnancy test and agree to use dual methods of contraception or abstain from sexual activity until the end of the study or for 120 days following the last dose of study drug, whichever is longer.
 
6) Male patients with female partners of childbearing potential must agree to use a highly effective method of contraception (vasectomy is acceptable) until the end of the study or for 120 days following the last dose of study drug, whichever is longer. All fertile men with female partners of childbearing potential should be instructed to contact the Investigator immediately if they suspect their partner might be pregnant at any time during study participation.
 
Exclusion Criteria
 
Patients will be excluded from the study if they meet any of the following criteria:
 
1) Poor tolerance to previous administration of AK002 in the opinion of the Investigator.2) Known hypersensitivity to any constituent of the study drug.3) Any disease, condition (medical or surgical), or cardiac abnormality, which, in the opinion of the Investigator, would place the patient at increased risk.4) Planned or expected vaccination with live attenuated vaccines during the treatment, or vaccination expected within 5 half-lives (4 months) of AK002 administration. All types and formulations of vaccines (including live attenuated vaccines) authorized by FDA or other regulatory authority for the prevention of COVID-19 may be administered before, during, or after this study. The vaccine should not be administered within 7 days prior to and within 7 days after the administration of AK002 so that any side effects caused by either of the 2 medications can be more easily determined.5) Women who are pregnant, breastfeeding, or planning to become pregnant while participating in the study.6) Any other reason that in the opinion of the Investigator or Medical Monitor makes the patient unsuitable for enrollment.

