7.4 Exclusion Criteria

Patients will be excluded from the study if they meet any of the following criteria:

- 1) Poor tolerance to previous administration of AK002 in the opinion of the Investigator.
- 2) Known hypersensitivity to any constituent of the study drug.
- 3) Any disease, condition (medical or surgical), or cardiac abnormality, which, in the opinion of the Investigator, would place the patient at increased risk.
- 4) Planned or expected vaccination with live attenuated vaccines during the treatment period, or vaccination expected within 5 half-lives (4 months) of AK002 administration. All types and formulations of vaccines (including live attenuated vaccines) authorized by FDA or other regulatory authority for the prevention of COVID-19 may be administered before, during, or after this study. The vaccine should not be administered within 7 days prior to and within 7 days after the administration of AK002 so that any side effects caused by either of the 2 medications can be more easily determined.
- 5) Women who are pregnant, breastfeeding, or planning to become pregnant while participating in the study.
- 6) Any other reason that, in the opinion of the Investigator or Medical Monitor, makes the patient unsuitable for enrollment.

8. Concurrent Medications

Prior and concomitant medications include both prescribed and over-the-counter medications and will be recorded in the electronic Case Report Forms (eCRF). Medications taken for EG/EoD or symptoms of EG/EoD, as well as any medications taken within 30 days prior to extension study Day 1 should be recorded.

Medications taken prior to the study should be maintained, as much as possible. Patients should be advised against taking any new medication or stopping an existing medication, both prescribed and over-the-counter, without consulting the Investigator, unless the change is required for emergency use. Immediately prior to the first infusion, the study site personnel should ensure that the patient continues to meet the inclusion criteria and none of the exclusion criteria (including use of prohibited medications as per AK002-016 criteria).

All medications used during the conduct of the study must be documented.

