11.4.4 Effective Methods of Contraception for Allakos Studies

This section applies to study subjects who are women of childbearing potential (WOCBP) and male study subjects whose sexual partners are WOCBP.

Abstinence is the only birth control method that is 100% effective in preventing pregnancy. For subjects who do not practice abstinence, Allakos recommends that study subjects use highly effective methods of contraception, which include:

- **Permanent Sterilization:** Tubal ligation, vasectomy – 99% effective
- **Long-Acting Reversible Contraceptives (LARC):**
 - IUD – 99% effective
 - Implantable rod (matchstick sized rod that contains progestin hormone implanted under the skin of the upper arm; prevents ovulation) – 99% effective
- **Contraceptive Injection:**
 - Intramuscular or subcutaneous injection of progestin hormone every 3 months – 96% effective
- **Short-Acting Hormonal Methods:**
 - Oral contraceptives or patch – 91% effective
 - Vaginal contraceptive ring (releases 2 hormones, progestin and estrogen, to prevent ovulation) – 91% effective

Note: Effectiveness rates obtained from the Birth Control Guide on the FDA web site ([FDA, 2021](#)).

Barrier and other methods not listed above when used together as dual methods such as a condom + diaphragm or condom + spermicide are less effective methods, therefore these dual methods are not recommended as they could increase the risk of becoming pregnant during the study or follow-up period. When using dual methods, at least 1 of the methods should be a highly effective method of contraception.

Subjects, who entered the study using dual methods of contraception that do not include at least 1 of the highly effective methods of contraception, are allowed to continue in the study but must be informed of the risks of not using highly effective methods of contraception.

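### Inclusion criterion 5 lets a woman of childbearing potential enter on a barrier-only contraceptive pair that Section 11.4.4 advises against

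*Combined protocol and SAP*

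**What the plan says.** Section 7.3, criterion 5, sets the contraception rule for women. A woman of childbearing potential must "agree to use dual methods of contraception or abstain from sexual activity until the end of the study", or for 120 days after the last dose if that is longer. The synopsis repeats it: a female patient must, "if of childbearing potential, have a negative pregnancy test and agree to use dual methods of contraception or abstain from sexual activity", for the stated period. Neither place defines the two methods or points to another section.

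Section 7.2 makes the criteria decisive: patients who complete a parent study and "meet the inclusion criteria in Section 7.3 and none of the exclusion criteria in Section 7.4 will be eligible for enrollment". Section 8 repeats the check immediately before the first infusion, when "the study site personnel should ensure that the patient continues to meet the inclusion criteria and none of the exclusion criteria".

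Section 11.4.4 gives the protocol's view of contraceptive methods and states its own scope: "This section applies to study subjects who are women of childbearing potential (WOCBP) and male study subjects whose sexual partners are WOCBP". It recommends highly effective methods and lists them with effectiveness figures. Of barrier pairs it says that "condom + diaphragm or condom + spermicide are less effective methods, therefore these dual methods are not recommended". It then advises that a patient using two methods should have at least one from the highly effective group. Subjects who came in on a pair without such a method may stay in the study, provided they are told of the risks.

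**The concern.** The text that decides entry does not carry the standard that the protocol sets out elsewhere. A site that applies criterion 5 correctly can admit a woman on condom with diaphragm, or condom with spermicide. Section 11.4.4 advises against these pairs because of pregnancy risk. What is at stake is a patient's protection against a pregnancy exposed to AK002 during 18 monthly infusions and the period after them. No estimate, test or error rate is involved.

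**Working it through.** No arithmetic establishes this point, and the plan gives no figure to reproduce. The check sets the texts side by side.

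1. **Does a barrier-only pair meet criterion 5?** Criterion 5 asks for two methods, or abstinence. Condom with spermicide is two methods, and Section 11.4.4 itself classes such a pair as dual methods. It qualifies.

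2. **What does Section 11.4.4 say of the same pair?** That it is less effective, is not recommended, and could raise the risk of pregnancy during the study or follow-up.

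3. **Which text decides entry?** Section 7.2 refers to Sections 7.3 and 7.4. Section 8 refers to the inclusion and exclusion criteria. Neither refers to Section 11.4.4, and nor does criterion 5.

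4. **Does Section 11.4.4 bind at entry?** Its statements on choice of method are advisory: it recommends, and it says what should be done. Its one mandatory statement is that subjects who entered without a highly effective method must be informed of the risks. That applies after entry and does not prevent it.

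5. **What do the other safeguards do?** Section 11.4.3 requires a urine test before each infusion and stops dosing if it is positive. Section 13.7.3 requires pregnancies to be reported within 24 hours. Both act once a pregnancy exists. Exclusion criterion 5 removes women who plan a pregnancy but does not address method failure. The last scheduled test is 35 days after the last dose, while the contraception duty runs to 120 days (follow-up ends at 84 days, so 120 is the longer period). That leaves 120 − 35 = 85 days in which contraception is required but no test is scheduled.

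6. **Can the size be computed?** The excess number of pregnancies would be the number of new entrants on barrier-only pairs, multiplied by the difference in pregnancy risk between such a pair and a pair that includes a listed method. Section 11.4.4 gives 99% (sterilisation, IUD, implant), 96% (injection) and 91% (pill or patch, ring) for the listed methods, a range of 91% to 99%. It gives no figure for barrier pairs. The number of women on such pairs and the number of entrants still to come are not stated. The product cannot be formed, and the point does not depend on it.

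**The case against.** The strongest reply is that Section 11.4.4 already handles this. It states that it applies to women of childbearing potential, takes up the same term as criterion 5, names the weak pairs and says that one method should be highly effective. Inclusion criterion 4 also requires willingness to comply with study procedures. Part of this stands: sites do have the advice, and counselling is mandatory for those who entered without a highly effective method. But willingness to follow procedures does not turn a recommendation into an entry condition.

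A second reply is that the sponsor foresaw the case and chose counselling over exclusion. The allowance is written in the past tense and concerns subjects who had entered on such pairs. It reads more naturally as a provision for women already in the study than as a decision to go on admitting them. The proposed change leaves it intact for those women.

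A third reply is that few women may be affected. That stands. All patients come from two parent studies whose contraception rules are not in these documents.

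A reader might also infer that the rule is weaker for women than for men, because criterion 6 requires a highly effective method of male patients with partners of childbearing potential. The documents do not support that as an overall comparison. Criterion 5 asks for two methods and a negative test, or abstinence; criterion 6 asks for one method. Counting which barrier pairs each criterion admits does not settle it either, because that count uses Section 11.4.4 to interpret criterion 6 and ignores it when reading criterion 5.

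**Conclusion.** The point holds as a gap between a binding entry criterion and the protocol's own advice. Followed as written, the plan can admit new women on a pair that Section 11.4.4 calls less effective. It is worth correcting because the remedy is cheap and applies a standard that the protocol already states. Its size in pregnancies or patients is unknown, and the analysis is unaffected. The conclusion assumes that entry is still open to some patients and that no document outside this one, such as the consent form, already imposes the stricter rule.

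Two stronger readings should be resisted. A reader might call this a contradiction. It is not one, since a recommendation and a looser requirement can both be met. A reader might also make something of the different descriptions of postmenopausal status in criterion 5 and Section 11.4.3, where only the latter adds an FSH threshold. No pregnancy risk is shown for that group, and removing the FSH condition could reduce pregnancy testing, so it forms no part of this finding.

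**What to change.** In criterion 5, in both Section 7.3 and the synopsis, keep the two-method requirement and add for new entrants: *at least one of which is a highly effective method listed in Section 11.4.4*. In Section 11.4.4, state that the allowance to continue with counselling covers only subjects already enrolled when the change takes effect. Section 10.1 already defines enrolment as receipt of the first open-label dose, so the cut-off needs no new definition.

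The cost is one clause in two places and one phrase in Section 11.4.4. A few new entrants on barrier-only pairs would have to add a listed method or abstain. No enrolled patient would be removed, and no procedure, visit or analysis changes.

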7.4 Exclusion Criteria

Patients will be excluded from the study if they meet any of the following criteria:

- 1) Poor tolerance to previous administration of AK002 in the opinion of the Investigator.
- 2) Known hypersensitivity to any constituent of the study drug.
- 3) Any disease, condition (medical or surgical), or cardiac abnormality, which, in the opinion of the Investigator, would place the patient at increased risk.
- 4) Planned or expected vaccination with live attenuated vaccines during the treatment period, or vaccination expected within 5 half-lives (4 months) of AK002 administration. All types and formulations of vaccines (including live attenuated vaccines) authorized by FDA or other regulatory authority for the prevention of COVID-19 may be administered before, during, or after this study. The vaccine should not be administered within 7 days prior to and within 7 days after the administration of AK002 so that any side effects caused by either of the 2 medications can be more easily determined.
- 5) Women who are pregnant, breastfeeding, or planning to become pregnant while participating in the study.
- 6) Any other reason that, in the opinion of the Investigator or Medical Monitor, makes the patient unsuitable for enrollment.

8. Concurrent Medications

Prior and concomitant medications include both prescribed and over-the-counter medications and will be recorded in the electronic Case Report Forms (eCRF). Medications taken for EG/EoD or symptoms of EG/EoD, as well as any medications taken within 30 days prior to extension study Day 1 should be recorded.

Medications taken prior to the study should be maintained, as much as possible. Patients should be advised against taking any new medication or stopping an existing medication, both prescribed and over-the-counter, without consulting the Investigator, unless the change is required for emergency use. Immediately prior to the first infusion, the study site personnel should ensure that the patient continues to meet the inclusion criteria and none of the exclusion criteria (including use of prohibited medications as per AK002-016 criteria).

All medications used during the conduct of the study must be documented.

8.1 Prohibited Medications

Any biologics or other medications that may interfere with the study, such as immunosuppressive or immunomodulatory drugs (i.e., azathioprine, JAK inhibitors, 6-mercaptopurine, methotrexate, cyclosporine, tacrolimus, anti-TNF, anti-IL-5, anti-IL-5 receptor, dupilumab, anti-IgE antibodies, omalizumab) are prohibited. The use of systemic or topical corticosteroids with a dose of >10 mg/day of prednisone or equivalent is prohibited unless it is due to unforeseen circumstances when it is deemed medically necessary to treat an unrelated medical condition or when given as a premedication prior to infusion or to treat an IRR that occurs during infusion.

There may be circumstances when the use of some of these medications during the study may be acceptable. In these cases, approval must be obtained from the Allakos Medical Monitor. An EGD may not be performed or may be delayed if a prohibited medication is started during the course of the study, at the discretion of the Medical Monitor.

8.2 Allowed Medications

Medications, other than those that are prohibited (Section 8.1), such as antihistamines, PPI, leukotriene antagonists, and sodium cromolyn are allowed during the study and, unless required due to unforeseen medical necessity, doses are to remain stable.

Systemic or swallowed corticosteroids with a dose of ≤ 10 mg/day prednisone or equivalent are acceptable, as long as the dose remains stable throughout the study. The use of systemic or topical corticosteroids with a dose of >10 mg/day of prednisone or equivalent is permitted if it is deemed to be medically necessary to treat an unrelated medical condition or when given as a premedication prior to infusion or to treat an IRR that occurs during infusion.

There may be circumstances when it is deemed medically necessary to alter (or start/stop) the dose of an allowed medication. If this medication is used to treat an unrelated medical condition, it is not a deviation from the protocol.

All medication use will be documented in the eCRF.

9. Study Treatment

9.1 Formulation of Test Product

AK002 is a humanized non-fucosylated IgG1 monoclonal antibody directed against Siglec-8.

AK002 drug product is supplied as a sterile liquid in a single-use 10R glass vial with a fill volume of not less than 10 mL. The product is stored at 2°–8°C.

The AK002 formulation is [REDACTED]

[REDACTED] pH 6.0, in sterile WFI.

Note: AK002 will be referred to as “study drug.” There is no placebo in the extension study.

9.2 Study Drug Packaging and Labeling

AK002 drug product is supplied as a sterile liquid in a single-use 10R glass vial with a minimum fill volume of approximately 10 mL. Each vial will be labeled with the required investigational use statement, lot number, Sponsor name, and directions for storage. Each vial will also contain a tear-off label with lot and/or kit number and space to document the patient identification (PID) number and preparation date. This tear-off label should be applied to the Investigational Product Dose Calculation and Preparation Worksheet and maintained with the source documents.

Glass vials are plugged with Teflon-coated rubber stoppers and sealed with aluminum seals.

9.3 Supply of Study Drug to the Investigational Site

The Sponsor (or designee) will ship study drug to the investigational sites. The initial study drug shipment will be shipped after all required regulatory documentation and approvals have been received by the Sponsor, and the contract has been executed. Subsequent study drug shipments will be triggered automatically based on predetermined supply levels and enrollment activity at the site.

